Visit 1 and Visit 2: Visit 1 is planned 12 months (Year 1) after the parent study last visit and Visit 2 is planned 24 months (Year 2) after the parent study last visit. The visits should be planned as close to the yearly date as possible, but as a maximum, fall within a window of ± 30 days. Visit 1 and 2 are planned relative to parent study last visit; therefore, participants with a gap period between the parent study last visit and extension Baseline will have less than 12 months between the extension Baseline and Visit 1 and less than 24 months between extension Baseline and Visit 2.

Early Withdrawal: In the event of early discontinuation from the extension study, the participants will be invited for an Early Withdrawal visit as soon as possible. Visit schedules for efficacy and safety assessments are detailed in the Schedule of Activities (Section 1.3). In case the participant is not willing or cannot return to the site for the Early Withdrawal visit, a telephone call will be organized to obtain the reason for withdrawal and AEs reporting.

Unscheduled visits: A participant may return for an unscheduled visit at the discretion of the Investigator and these visits may include assessments as described in the Schedule of Activities (Section 1.3). If a participant experiences a relapse requiring treatment with steroids or switching to other DMD, a blood sample will be taken before administration of these drugs, irrespective of

time left for the next scheduled visit and blood sample collection, and irrespective of participant continuing or discontinuing the study. Further assessments and management of relapse are at the discretion of the physician.

The data from scheduled and unscheduled visits will be collected in the electronic case report form (eCRF). The schema and visit schedules for efficacy and safety assessments are detailed in the study schema (Section 1.2) and the Schedule of Activities (Section 1.3).

The planned study duration for each participant is 2 years (see Section 1.2). The study aims to enroll the first patients in Q1 2021 and have the Last Patient Last Visit in Q4 2023.

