- 6-months confirmed disability progression (6MCDP), is used in the IAP to keep consistent with the parent study IAP, although 3 months confirmed disability progression, 3MCDP, is defined in the CSP.
- As data provided from MRI vendor only contains absolute values for (all) T1-Gd+ lesions per assessment (no new T1-Gd+ lesions), in consequence (all) T1-Gd+ lesions per assessment will be used for definition of disease activity and for calculation of Combined Unique Active (CUA) lesions during MAGNIFY MS Extension Study. However, as MAGNIFY MS Extension Study only has yearly MRI assessments the number of "new" and "all" T1-Gd+ lesions can be considered identical (see also explanation in Section 9.8).

8 Analysis Sets and Subgroups

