9.5 Time Window

- Day 1 is the day of start of study medication at MAGNIFY MS Baseline Visit, the day before is Day -1 (no Day 0 is defined).
- Study day is defined relative to Day 1.

The visit schedule in the Extension Study is defined as follows:

- 1 month = 30 days,
- 1 year = 360 days,

relative to the M24 Visit in the parent study.

- MAGNIFY Extension Baseline Visit: The visit is planned to coincide with or be as near to M24 as possible to minimize the transition gap period, it may also be the same visit as M24.
- Visit 1: 1 year ((360 days) after M24 Visit (\pm 30 days)
- Visit 2: 2 years (720 days) after M24 Visit (± 30 days)

Visit 1 and Visit 2 will also be referred to as the M36 Visit and the M48 Visit, respectively, in the following sections of this IAP as well as in the Tables, Listings, and Figures (TLF) outputs, for consistent presentation of analyses and results over time. Footnotes will be added in the TLF outputs to clarify that these Visits are to be understood as nominal Visits.

In each analysis, should an assessment be delayed, participants' assessment data will be treated as though it occurred at the nominal time point specified (i.e., data collected out of visit windows will not be excluded or adjusted in any analysis) and inferences will be conducted accordingly. Thus, further time windows will not be specified. The MRI assessment will be the only exception to this rule. Handling of out-of-window MRI assessments is discussed in Section 9.8.

All observations from unscheduled visits will be included only in the analyses of visit independent summaries (e.g., counts of AEs, concomitant medications and procedures, relapse reporting and EDSS) unless for the last assessment available. In this case the missing Early Withdrawal (EW) visit will be imputed by the unscheduled visit.

The assessments of the EW visit will be mapped to the nearest planned post-baseline visit with a missing assessment before or after the EW visit of the individual assessment for all statistical analyses and descriptive summaries. As not all assessments of the EW are performed at each visit, the different assessments of the EW can be assigned to different visits. If the duration (in days) between the EW visits and two missing planned visits are equal, then the assessment will be assigned to the later visit.

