10.1 Disposition of Participants and Discontinuations

This section describes participant disposition in the extension study.

Participant disposition in this Extension Study will be presented for the ES:

- Total number of participants enrolled in the MAGNIFY MS Extension Study (i.e., participants who gave informed consent for the Extension Study)
- Number of participants who discontinued in the Screening phase by the main reason:
 - o Subject did not meet all eligibility criteria
 - Withdrawal by subject
 - o Progressive Disease
 - o Adverse Event
 - Lost to Follow-up
 - Death
 - o Other
- Number of eligible participants in the Extension Study, overall and by the following categories:
 - Number and percentage of eligible participants enrolled before the start of COVID-19
 - Number and percentage of eligible participants ongoing at data cut-off (applicable to IAs only)
 - o Number and percentage of eligible participants who completed the study
 - Number and percentage of eligible participants who discontinued the study, with the primary reason of discontinuation:
 - Withdrawal by subject

- Progressive disease
- Adverse event
- Lost to follow-up
- Death
- Protocol non-compliance
- Other

The duration of gap period between MAGNIFY MS Trial and MAGNIFY Extension Study Baseline will be summarized using the following classes:

- o No gap (i.e., Month 24 Visit and Extension Baseline coincide)
- o Duration of gap period < 1 month
- o Duration of gap period ≥ 1 month and ≤ 3 months
- o Duration of gap period ≥ 3 months and < 6 months
- O Duration of gap period ≥ 6 months and ≤ 9 months
- o Duration of gap period ≥ 9 months and ≤ 12 months
- o Duration of gap period > 12 months

Additionally, duration of gap period will be summarized using descriptive statistics.

Percentages will be presented with respect to the number of eligible participants.

The number of participants in each analysis set will be provided overall, by region, by country within region and by site.

The following participant data listings will be provided:

- Listing of discontinued participants for the FAS,
- Listing of participants excluded from the Analysis Sets.

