14.1.1 Primary Objective: Derivation and analysis of the primary endpoint

No Evidence of Disease activity (NEDA), also referred to as freedom from disease activity, is a new goal that is emerging in MS treatment. NEDA is a composite measure of disease activity, including relapses, cognition and disability progression, and MRI activity.

NEDA-3 during the Extension Study Period is defined as absence of the following three events during the Period:

- Qualifying Relapses
- 6-months Confirmed Disability Progression (6MCDP, see definition below)
- MRI Activity (i.e., presence of T1 Gd+ lesions and/or active T2 lesions)

NEDA-3 will be analyzed with the Kaplan-Meier (KM) time-to-event method to reduce the impact of unknown/missing information.

The start date will be the end date of M24 Visit + 1.

The event date will be defined as the minimum of

- the onset date of the first qualifying relapses during the Extension Study Period
- the start date of the first 6MCDP during the Extension Study Period (see definition below)
- the scan date of the first MRI during the Extension Study Period where at least one T1 Gd+ lesion or at least one active T2 lesion (see Section 9.8 for definition) is identified.

Imputation of partial onset dates of relapses is described in Section 9.7. Since full dates of MRI scan and EDSS assessment are mandatory, partial dates of 6MCDP, or MRI Activity are not expected.

If the participant did not experience any of the three events described above during the Extension Study Period, the minimum of the scan date of the last available MRI, the assessment date of the last available EDSS, and the Extension Study completion/discontinuation date will be used as the censoring date.

The time to disease activity (in months) will be calculated as [event date or censoring date as applicable – start date + 1]/30.4375. The number of participants at risk, failed, and survival rate (i.e., the proportion of participants with NEDA-3) along with the 95% CI will be estimated as per the KM method and reported at 6-months intervals. The KM survival curve will be plotted as well.

A descriptive summary of number and proportion of participants with event (overall and by type of event, i.e., qualifying relapse, 6MCDP, or MRI activity as the earliest event) and censored will be also presented.

6MCDP

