The 6MCDP during Extension Study Period is defined as sustained increase in EDSS score that started during the Period. A Sustained Increase in EDSS score is defined by an increase of:

- at least 1.5 points if the Baseline EDSS score was 0, or
- at least 1 point if Baseline EDSS score was between 0.5 and 4.5 inclusively, or
- at least 0.5 point if the Baseline EDSS score was at least 5,

that occurs over a 6-months' time-period.

The increase will be defined as sustained when it occurs on two post-Baseline Visits during the Extension Study Period that are at least 166 days apart (to be consistent with the parent study minimum visit gap) and no observations at any other visits (including unscheduled visits) in between are less than the defined increase. The assessment date of the earlier of the two EDSS assessments with the defined increase will be defined as the start date of 6MCDP.

For descriptive summaries the following rules will be defined:

Qualifying Relapse

- Yes: any qualifying relapse reported during the Extension Study Period,
- No: Extension study period completed, and no qualifying relapse reported during the Extension Study Period,
- Unknown: otherwise.

6MCDP

• Yes: sustained increase in EDSS score that started during the Extension Study Period,

- No: at least 2 post-Baseline EDSS assessments that are 166 (or more) apart and no sustained EDSS progression that started during the Extension Study Period,
- Unknown: Otherwise.

MRI activity

- Yes: any T1-Gd+ or active T2 observed during the Extension Study Period,
- No: at least one post-Baseline MRI and no T1-Gd+ or active T2 observed during the Extension Study Period,
- Unknown: otherwise.

Analysis (Analysis Set)	Derivation	Statistical Analysis Methods	Missing data handling		
	Primary endpoint: Proportion of participants with NEDA-3 during Year 3 Visit and Year 4 Visit Period after the initial dose of cladribine tablets				

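### Participants who leave for progressive disease without a recorded NEDA-3 event are censored as non-informative, and no readable sensitivity analysis tests this

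*SAP*

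**What the plan says.** **Events.** SAP 14.1.1: "NEDA-3 during the Extension Study Period is defined as absence of the following three events during the Period". The three are qualifying relapse, 6MCDP and MRI activity. Leaving the study is not an event, whatever the reason.

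**Censoring.** Without an event, the minimum of three dates applies: last available MRI, last available EDSS, and study completion or discontinuation. The sentence ends "the Extension Study completion/discontinuation date will be used as the censoring date". SAP 14.2.2 uses the same rule for time to first disease activity.

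**Reasons for leaving.** SAP 10.1 tabulates the "Number and percentage of eligible participants who discontinued the study, with the primary reason of discontinuation". Progressive disease and death are separate entries in that list. Neither document defines progressive disease.

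**Confirmation.** 6MCDP needs the EDSS increase at two visits within the Extension Study Period "that are at least 166 days apart (to be consistent with the parent study minimum visit gap"), with no lower score in between. SAP Section 7 records the change from the protocol's 3-month rule: "6-months confirmed disability progression (6MCDP), is used in the IAP to keep consistent with the parent study IAP".

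**Schedule.** SAP 9.5 puts Visit 1 at 360 days, and "Visit 2: 2 years (720 days) after M24 Visit", each ±30 days. Protocol 4.1: "In the event of early discontinuation from the extension study, the participants will be invited for an Early Withdrawal visit as soon as possible". MRI, EDSS and relapse reporting are scheduled at that visit (Protocol Table 2). A participant who cannot or will not attend is telephoned for the reason and for adverse events only.

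**Missing data.** Protocol Table 6 assumes missing at random (MAR) and defers methods for departures from it to the SAP. SAP 14.1.2 lists a repeat on the Treatment Completer Set, a subgroup analysis by previous DMD treatment, and crude percentages with missing outcomes shown as their own category.

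**The concern.** Kaplan-Meier gives a censored participant the later risk of those still under observation. That is reasonable for someone who moves away. It is hard to defend for someone whose recorded reason for leaving is worsening of the disease that the endpoint measures.

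The confirmation rule adds to this. A leaver may have a real EDSS rise that never becomes a 6MCDP because no second score at least 166 days later is taken. If that person also has no recorded relapse or lesion, the worsening contributes nothing to the event count.

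The study has one arm, so the absolute NEDA-3 proportion is the result, and no comparator offsets an upward bias. Two of the three analyses in SAP 14.1.2 reuse the same censoring. The third separates out missing outcomes but does not link them to the reason for leaving.

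**Working it through.** **1. Whether the plan has a figure to reproduce.** It does not. The readable text gives no expected NEDA-3 rate, dropout rate or number leaving for progressive disease, and the sample-size basis is blacked out. Protocol 1.1 gives at most 256 enrolled for 200 to 220 evaluable. The shortfall is 1 − 220/256 = 14.1% to 1 − 200/256 = 21.9%. That is not a dropout forecast, because 256 is a maximum and evaluable is not defined in the readable text.

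**2. When leaving blocks confirmation** (days after the parent study Month 24 visit).
- A rise first seen at the Early Withdrawal visit cannot be confirmed.
- A rise first seen at Visit 1 on day 360 needs a further EDSS on or after day 360 + 166 = 526. With the ±30-day window this becomes day 496 to 556. A last EDSS before then blocks confirmation; a later one does not.
- A completer whose first rise is at Visit 2 is blocked in the same way.

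**3. Effect on the Kaplan-Meier estimate.** Let k of N participants be eventless progressive-disease leavers. Assumptions not in the documents: N = 256 or 210; 24-month NEDA-3 among all others p = 50% to 80%; their events found at months 12 and 24 with equal yearly hazard h = 1 − √p; no other dropout; leaving at month 6 or month 18.

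With no other dropout, moving k leavers at time t from censored to event lowers the estimate by

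shift = (k/N) × S(24)/S(t),

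where S(24)/S(t) is the chance that someone event-free at t stays so to month 24. It equals p for leaving at month 6 and √p for leaving at month 18. It cannot exceed 1, so under these conditions the shift cannot exceed k/N.

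**4. One case in full:** N = 256, p = 0.70, k = 10, leaving at month 18. The others number 246 and h = 1 − √0.70 = 0.1633.
- Month 12: 246 × 0.1633 = 40.2 events, 256 at risk, S = 1 − 40.2/256 = 0.843.
- Leavers censored: at month 24 the factor is 0.8367, so S(24) = 0.843 × 0.8367 = 70.5%.
- Leavers as events: at month 18 there are 256 − 40.2 = 215.8 at risk, factor 1 − 10/215.8 = 0.9537, so S(24) = 0.843 × 0.9537 × 0.8367 = 67.3%.
- Shift 3.3 points before rounding. Formula: (10/256) × 0.8367 = 3.3 points.
- Greenwood SE, leavers censored: 0.705 × √[40.2/(256 × 215.8) + 33.6/(205.8 × 172.2)] = 0.0289, so the 95% half-width is 1.96 × 0.0289 = 5.7 points.

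**5. Range.**

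| k | Lowest (N = 256, p = 0.5, month 6) | N = 256, p = 0.7, month 18 | Highest (N = 210, p = 0.8, month 18) |
|---|---|---|---|
| 2 | 0.4 | 0.7 | 0.9 |
| 5 | 1.0 | 1.6 | 2.1 |
| 10 | 2.0 | 3.3 | 4.3 |
| 20 | 3.9 | 6.5 | 8.5 |

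Entries are percentage points. Across all scenarios the 95% half-width with leavers censored runs from 4.9 to 7.1 points. The shift becomes comparable with it only near 20 leavers.

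**The case against.** A reader might go further and infer that everyone who leaves for progressive disease is counted as free of disease activity. The documents do not support that. A recorded relapse, lesion or 6MCDP is already an event, and the Early Withdrawal visit includes MRI, EDSS and relapse reporting. Those with no event are censored and given the later risk of those who stay; they are not scored as NEDA-3.

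A reader might also infer that leaving always prevents confirmation. It does so only when the first rise is under 166 days before the last EDSS. Completers with a first rise at Visit 2 share the problem, so it belongs to the confirmation rule and not only to discontinuation.

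Nor is the recorded reason shown to be the outcome itself. The term is undefined, and "Progressive Disease" also appears among the screening-phase reasons in SAP 10.1, as a generic disposition category would.

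Numbers may be small. Protocol 6.5 restricts no therapy, so worsening or a switch to another DMD does not require leaving. The study is exploratory with no formal hypothesis. The disposition table will show how many leave for this reason, and the crude summary codes a leaver with no relapse as unknown for relapse, not as relapse-free.

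All of this stands, and it limits the point to eventless leavers and to a supportive analysis. It does not remove the gap. The disposition table does not say how many leavers were eventless, and no readable analysis in 14.1.2 varies the censoring assumption. The SAP lists abbreviations for censoring at random and not at random and cites two papers on sensitivity to informative censoring. A blacked-out section might use them, but 14.1.2 is readable and is where the primary endpoint's sensitivity analyses are set out.

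**Conclusion.** The concern holds for eventless leavers with primary reason progressive disease. Censoring them as non-informative is implausible, and the likely direction is an upward bias in NEDA-3 and a longer time to first disease activity. The size is unknown, because the documents give no count. Under the assumptions above it is about 1 to 2 points for 5 leavers and 2 to 4 for 10, inside a 95% half-width of about 5 to 7 points. That justifies a supportive analysis, not a change to the primary one. It is one specific case of a wider gap: the protocol defers methods for departures from MAR to the SAP, and the readable SAP supplies none for the primary endpoint.

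**What to change.** Add one sensitivity Kaplan-Meier analysis to SAP 14.1.2 and repeat it for 14.2.2. Count a participant with no recorded relapse, MRI activity or 6MCDP and with primary reason progressive disease as an event at the discontinuation date. State that this date replaces the minimum-of-three-dates rule for them, so that they stay at risk until they leave. Keep the primary analysis unchanged, and report the number reclassified beside the result. If there are none, one sentence closes the matter.

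Deaths can be treated the same way only through what is recorded: the discontinuation category for death, or an adverse event with fatal outcome. The disposition list in SAP 10.1 has no category for death attributed to MS, so the rule should not depend on that label.

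The cost is one extra run per endpoint on a reason already collected. The drawback is that the reason is undefined and presumably rests on the investigator's judgement, so the result is supportive only.

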9.4 Conversion Factors

The following conversion factors will be used to convert days into months or years for all observations except Visit related dates:

- 1 month = 30.4375 days,
- 1 year = 365.25 days.

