14.2.2 Time to First Disease Activity

Time to first disease activity is defined as the time to first occurrence of either qualifying relapse, or 6MCDP, or new or enlarging T2-hyperintense lesions (active T2 lesions), or new T1 Gd+ lesions. This will be evaluated for the following Periods with corresponding start dates defined below:

- Extension Study Period
 - Start date for time to first disease activity: end date of M24 Visit + 1 (as defined in Section 14.1.1)
- Parent and Extension Study Period

o Start date for time to first disease activity: date of Day 1 (as defined in Section 9.5)

Since events described above are the same events as in NEDA-3 definition, the event date will be defined the same as in Sections 14.1.1 or 14.2.1, accounting for only events started during the above Periods, respectively. If the participant did not experience any disease event during a Period, the minimum of the scan date of the last available MRI during this Period, the assessment date of the last available EDSS during this Period, and the Extension Study completion/discontinuation date will be used as the censoring date.

Time to first disease activity (in months) will be calculated as [event date or censoring date as applicable – start date of the Period + 1]/30.4375 and the 5%, 10%, 15%, 25% percentile and median time to first disease activity will be estimated using the KM method along with the 95% CI.

Analysis (Analysis Set)	Derivation	Statistical Analysis Methods	Missing data handling
Secondary er	ndpoint: Time from M24 Visit to	o first disease activity	
Secondary (FAS)	Time to event: [event date or censoring date as applicable – start date + 1]/30.4375 for disease activities started during Extension Study Period	KM time-to-event: 5%, 10%, 15%, 25% percentiles and Median time to disease activity will be estimated as per the KM method and reported along with the corresponding 95% CI.	Same as Section 14.1.1
Secondary (FAS by subgroup "Previous treatment with DMDs")	Same as above	Same as above with KM estimates reported by subgroup.	Same as Section 14.1.1
Secondary er	ndpoint: Time from initial dose	of cladribine tablets to first diseas	e activity
Secondary (FAS)	Time to event: [event date or censoring date as applicable – start date + 1]/30.4375 for	Same as above.	Same as above.
Secondary (FAS by subgroup "Previous treatment with DMDs")	disease activities started during Parent and Extension Study Period		

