 - Censoring date: participants with no active T2 lesion identified at any scans during the Extension Study Period will be censored at the scan date of the last available MRI during this Period
- first new T1 Gd+ lesion
 - Event date: the scan date of the first MRI during the Extension Study Period where at least one new T1 Gd+ lesion (see Section 9.8 for definition) is identified
 - Censoring date: participants with no new T1 Gd+ lesion identified at any scans during the Extension Study Period will be censored at the scan date of the last available MRI during this Period
- first 6MCDP, as measured by EDSS
 - Event date: the start date of the first 6MCDP during the Extension Study Period (see definition in Section 14.1.1)
 - Censoring date: participants with no 6MCDP started during the Extension Study Period will be censored at the assessment date of the last available EDSS during this Period
- first qualifying relapse
 - Event date: the onset date of the first qualifying relapse during the Extension Study Period
 - Censoring date: participants with no qualifying relapse reported during the Extension Study Period will be censored at the Extension Study completion/discontinuation date
- treatment start with other DMDs

- Event date: the start date of the first other DMDs used during the Extension Study Period
- Censoring date: participants who did not use any other DMDs during the Extension Study Period will be censored at the Extension Study completion/discontinuation date

A recurrent event analysis will be performed on all qualifying relapses using the Mean Cumulative Function (MCF) method, where MCF(t) represents the mean cumulative number of relapses up to time t. The MCF estimate for recurrent events will be calculated and plotted for all qualifying relapses. The MCF Nelson estimates will be presented for every month along with their 95% CIs. The increase in MCF in each month, defined as MCF(t) - MCF(t-1) will also be displayed.

Time (in months) from the initial dose of cladribine tablets (i.e. start date = date of Day 1 as defined in Section 9.5) to each event and to censoring (as defined below) will be calculated as [event date or censoring date – start date + 1/30.4375, and analyzed using the MCF method.

- recurrent qualifying relapse
 - Event date: the onset date of each qualifying relapse during the Parent and Extension Study Period

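### Yearly extension MRI cannot support the 6- and 18-month NEDA-3 rows, or percentile times from M24 to first MRI lesion

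*SAP*

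**What the plan says.** **Schedule.** Protocol 4.1 states "Visit 1 is planned 12 months (Year 1) after the parent study last visit and Visit 2 is planned 24 months" after it, and the Schedule of Activities lists MRI only at Visit 1 and at Visit 2/early withdrawal. SAP 9.5 turns this into days, with Visit 2 at "2 years (720 days) after M24 Visit" and Visit 1 at day 360, each ±30 days. SAP Section 7 confirms that the "MAGNIFY MS Extension Study only has yearly MRI assessments".

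**Dating.** In SAP 14.1.1 the MRI component of the event date is "the scan date of the first MRI during the Extension Study Period" that shows a T1 Gd+ or active T2 lesion. SAP 14.2.3 dates the single-lesion endpoints in the same way. For example, "participants with no new T1 Gd+ lesion identified at any scans during the Extension Study Period will be censored" at their last available scan.

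**Reporting.** The survival rate, which SAP 14.1.1 equates with the proportion with NEDA-3, is to be "estimated as per the KM method and reported at 6-months intervals" with a 95% CI. SAP 14.2.1 applies the same method to the Year 3 and Year 4 Visit Periods. The Year 3 result also enters the interim analysis (SAP 6.1). In SAP 14.2.2 the 5%, 10%, 15% and 25% "percentile and median time to first disease activity will be estimated using the KM method". SAP 14.2.3 carries this over to time to first active T2 and first T1 Gd+ lesion.

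No interval-censored method is planned, and no caveat is attached to time points that have no scan. The only related footnote says that visits are nominal (SAP 9.5).

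**The concern.** NEDA-3 needs all three components to be absent. A 6-month row that precedes every scheduled scan cannot show absence of MRI activity, yet it will be tabulated under the NEDA-3 label with a confidence interval. EDSS does little to fill the gap. It is scheduled at the same two visits. The Extension Baseline EDSS counts toward progression only for participants with a gap period (SAP 11.3). Unscheduled EDSS is required when a relapse is suspected, so it mostly concerns people who may already have an event.

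The percentile times for MRI lesions have a related problem. They are read as the time by which a given share of participants had a lesion, but on the M24 clock they can hardly be anything other than a visit date. These estimates are the product of an exploratory single-arm study, so a mislabelled row or a time set by the calendar is itself a misreported result.

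**Working it through.** **Inputs.** From the SAP: visits at days 360 and 720 ±30 (9.5); "1 month = 30.4375 days" (9.4); scan-date dating (14.1.1, 14.2.3). From the Protocol synopsis: 200 to 220 evaluable participants, taken as 210. Assumed, because the documents give no rates: MRI activity of 10%, 20% or 30% and relapse of 5%, 5% or 10% per 360-day year, with constant hazards. There is no figure in the plan to reproduce.

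**Step 1, calendar.** The scan windows are days 330-390, or 330/30.4375 = 10.84 to 390/30.4375 = 12.81 months, and days 690-750, or 22.67 to 24.64 months. Month 6 is 6 × 30.4375 = day 182.6 and month 18 is day 547.9. Neither is near a window.

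**Step 2, closed form.** Let m and r be the yearly MRI-activity and relapse proportions.
- True NEDA-3 at day d is [(1−m)(1−r)]^(d/360).
- The planned 6-month value is (1−r)^(182.6/360), because only relapses can have been dated.
- The planned 18-month value is about (1−r)^(547.9/360) × (1−m), because only one year of MRI activity has been seen.

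For m = 20% and r = 5%:
- 6 months: 0.95^0.507 = 0.974 against 0.76^0.507 = 0.870.
- 18 months: 0.95^1.522 × 0.80 = 0.740 against 0.76^1.522 = 0.659.

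**Step 3, simulation.** 400 runs of 210 participants, visits uniform within ±30 days, event-free participants censored at Visit 2, progression and dropout left out.

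| MRI / relapse per year | 6 months: planned vs true | Excess (points) | 18 months: planned vs true | Excess (points) |
|---|---|---|---|---|
| 10% / 5% | 97.5% vs 92.4% | 5.1 | 83.1% vs 78.7% | 4.4 |
| 20% / 5% | 97.4% vs 87.1% | 10.3 | 74.2% vs 65.9% | 8.3 |
| 30% / 10% | 94.8% vs 79.1% | 15.7 | 59.6% vs 49.6% | 10.0 |

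The planned 6-month value equals the relapse-only value in every row (97.5%, 97.4%, 94.8%). With visits within ±10 days the 6-month values are unchanged and the 18-month values are 83.1%, 73.8% and 59.6%.

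**Step 4, MRI-only percentile times (months from M24).**

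| MRI activity per year | | 5% | 10% | 15% |
|---|---|---|---|---|
| 10% | planned | 11.9 | 22.7 | 23.5 |
| | true onset | 5.8 | 11.8 | 18.2 |
| 20% | planned | 11.4 | 11.9 | 12.4 |
| | true onset | 2.7 | 5.6 | 8.6 |
| 30% | planned | 11.2 | 11.5 | 11.9 |
| | true onset | 1.7 | 3.5 | 5.4 |

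Every percentile obtained, including the 25% and the median, fell inside a visit window in every scenario. I omit those two from the table: at the lower rates they also depend on how the curve falls among the last participants scanned, which is a separate matter.

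**Step 5, composite percentiles.** Time to first disease activity includes relapses at their own onset dates, so its percentiles are mixed. At 30%/10% the 5% percentile is 5.8 months, almost always a relapse date. At 20%/5% the 10% and 15% percentiles are 11.4 and 11.9 months, essentially always in a visit window, while the 25% percentile is 15.3 months and lies in a window in about 61% of runs.

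**Step 6, exceptions.** Early-withdrawal scans can fall off the yearly grid. SAP 9.8 keeps a scan up to 185 days from its visit, so one as early as day 330 − 185 = 145 could count. Protocol 8.1 allows only ±5 days between visit and scan, so such cases should be few. Unscheduled MRIs for safety or a switch of DMD are read at the site (Protocol 8.1.1.1) and do not fill the gap in central reads.

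**The case against.** The study is exploratory and tests no hypothesis, and the Protocol's primary read-out is the Kaplan-Meier estimate at the end of two years (Protocol 9.4.1). No decision rests on months 6 or 18. The SAP says openly that the event date is the scan date, and step curves with scheduled imaging are conventional. To call the rows biased presumes that lesion onset is the target, which the SAP does not claim. It also plans separate Year 3 and Year 4 Visit Period analyses, counts by type of earliest event, and crude percentages by component (SAP 14.1.1, 14.1.2, 14.2.1). A careful reader could see that the early events are relapses.

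Much of this stands. It limits the consequence, and it is why the point stays with reporting and does not touch the design. But a plotted step curve differs from a table row that states a 6-month NEDA-3 proportion with a 95% CI. Even without lesion onset as the target, that row asserts absence of MRI activity before anyone has looked. The planned summaries by event type cover whole periods and do not relabel the 6- and 18-month rows, and the by-period analyses have a 6-month row of their own.

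Two further objections stand in full. Percentiles of the composite are not all visit dates. And on the clock that starts at Day 1, the parent study has visits at Months 1, 2, 3, 6, 12, 15, 18 and 24 (SAP 9.10), so the problem there is confined to the time after Month 24, for example months 30 and 42.

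**Conclusion.** The point holds on the M24 clock. The 6-month NEDA-3 row, in the primary analysis and in the Year 3 and Year 4 Visit Period analyses, is essentially a relapse-free proportion. The 18-month row in the primary analysis carries only MRI activity found by Visit 1. Under the assumed rates the overstatement is about 5 to 16 points and 4 to 10 points respectively. The size rests on those rates and on constant hazards; the direction does not. Percentile times from M24 to first active T2 and first T1 Gd+ lesion report the visit windows, apart from a few early-withdrawal or out-of-window scans.

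Three stronger readings are tempting and not supported:
- A reader might infer that the two-year primary figure is undermined. This argument does not reach it: month 24 is day 730.5, inside the Visit 2 scan window, so the figure is not read at a time remote from any scheduled scan.
- A reader might infer that all percentiles in SAP 14.2.2 and 14.2.3 are visit dates. Relapse and DMD start have their own dates, and the composite is a mixture.
- A reader might infer that the percentile intervals will look falsely tight. That does not hold generally: in one check with 210 participants at 15% MRI activity and 5% relapse, the interval for the composite 25% percentile ran from about 12.7 to 23.7 months.

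**What to change.** **SAP 14.1.1 and 14.2.1.** Report extension-period NEDA-3 with its 95% CI by nominal visit, meaning status through the Visit 1 and Visit 2 assessments. Drop the 6- and 18-month rows, and months 30 and 42 for the analyses that start at Day 1. In the 20%/5% example the reported quantities would then target 0.80 × 0.95 = 76% at Visit 1 and 0.76² = 57.8% at Visit 2.

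**SAP 14.2.2 and 14.2.3.** For M24-clock time to first active T2 and first T1 Gd+ lesion, replace percentile and median times by cumulative proportions at Visit 1 and Visit 2. For the M24-clock composite, give these proportions in place of the percentiles. Keep Kaplan-Meier percentiles for relapse and for start of another DMD.

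**Optional.** An interval-censored estimate for the MRI endpoints only. The interval would run from the later of the M24 start date and the last scan before the first active scan, to the first active scan. This also covers participants who entered with a Month 18 scan but no Month 24 scan. It is not proposed for the EDSS component, for which no interval rule is offered here.

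**Cost.** SAP wording and table shells; no new data and no change to conduct. The primary table will have fewer rows. The change does not resolve the separate limit that an EDSS rise first seen at Visit 2 cannot be confirmed within the extension, since 6MCDP needs two assessments at least 166 days apart.
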